9.1.3. Treatment Phase

Details of the procedures performed during the Treatment Phase are outlined in the Time and Events Schedule. Subjects should start study treatment within 72 hours after randomization. Subjects will be closely monitored for adverse events, laboratory abnormalities, and clinical response. Clinical evaluations and laboratory studies may be repeated more frequently, if clinically indicated. If disease progression is confirmed, then the subject will discontinue study treatment, complete the End-of-Treatment Visit, and enter the Follow-up Phase.

End-of-Treatment Visit

Unless a subject withdraws consent for study participation or is lost to follow up, an End-of-Treatment Visit is to occur 4 weeks after the last dose of study treatment for collection of adverse events for 30 days postdose, or as soon as possible before the start of subsequent therapy. Every effort should be made to conduct the End-of-Treatment Visit before the subject starts subsequent treatment. If a subject is unable to return to the site for the End-of-Treatment Visit, then the subject should be contacted to collect information on adverse events and concomitant medications used to treat adverse events as specified in Section 12.3.1, All Adverse Events. If the End-of-Treatment visit occurs before 30 days, then the subject should be contacted after 30 days so that all adverse events that occurred within the 30-day period are recorded. Additional information on reporting of adverse events is presented in Section 12, Adverse Event Reporting.

9.1.4. Follow-Up Phase

Each subject is to have a follow-up visit 8 weeks after the last dose of study treatment. Beyond 30 days after the last dose, serious adverse events considered related to study treatment will continue to be collected. For a subject who discontinues study treatment before disease progression, disease evaluations should continue to be performed as specified in the Time and Events Schedule. After disease progression is documented, survival status, subsequent anticancer treatment, response to subsequent anticancer treatment, and date of progression will be recorded. Information on all new second primary malignancies will also be collected until the end of the data collection period. If the information is obtained via telephone contact, then written documentation of the communication must be available for review in the source documents. If the subject has died, then the date and cause of death will be collected and documented on the eCRF.

Follow-up will continue until the end of the data collection period, approximately 24 months after the last subject was randomized or when median overall survival for both arms has been reached, whichever occurs first.

Continuation of Follow-up Phase study procedures is not required once the end of the data collection period is reached, and the End of Trial page of the eCRF should be completed at that time for subjects ongoing in the Follow-up Phase.

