Study drug (Dara-SC or Dara-IV)			X	X	X	X	X	X	X			
Predose and postdose medications			X	X	X	X	X	X	X			
Laboratory Assessments												
Blood group and type assessment and indirect antiglobulin test (IAT) results	Obtained before start of dose; includes ABO, Rh, and indirect antiglobulin test results. Results placed on subject identification wallet card		X									
Urine or serum pregnancy test	Women of childbearing potential only	Study day -14 to -1	As clinically indicated									
Chemistry	May be performed up to 3 days before study drug administration day. Results must be evaluated before each study drug administration. At Cycle 1 Day 1, tests do not need to be repeated if they were performed within the previous 5 days.	X	X				X		X	X		
Hematology		X	X	X	X	X	X	X	X	X		
HBV DNA test	Only for subjects who are positive for anti-HBc or anti-HBs	X	X				X		X	X		X ^b
Whole blood (biomarker)	Predose collection for immunophenotyping		C1				C4					
Whole blood (biomarker)	Predose plasma and PBMC collection		C1				C4 and C6		C13	X		
Pharmacokinetics and Immunogenicity Blood Samples												
Pharmacokinetics, immunogenicity	Pharmacokinetics of daratumumab; immunogenicity of daratumumab and rHuPH20		See Table 2									
Disease Evaluations (Blood/Urine) Samples must be sent to the central laboratory.												
Serum β_2 -microglobulin	SPEP and UPEP are to be performed within 14 days before Cycle 1 Day 1. See Section 9.2.2 for details.	X										
Qlg (IgA, IgM, IgG, IgD, IgE)		X	Every 3 months (\pm 1 month) during treatment							X		
SPEP		X	X				X		X	X	X ^a	
UPEP (24-hr urine sample)		X	X				X		X	X	X ^a	

Study Day	Notes	Study Visits										
		Screening Phase	Treatment Phase (1 Cycle = 28 days)							Follow-up Phase		
			Cycles 1 & 2				Cycles 3-6		Cycles 7+	EOT	FUP ^a	Survival ^a
			-28 to -1	D1	D8	D15	D22	D1	D15	D1 ^c	Post-Treatment Week 4 +7 days	Post-Treatment Week 8 ±7 days
Serum calcium corrected for albumin		X	X					X		X	X	
Serum FLC & serum/urine immunofixation		X	Serum FLC and serum/urine immunofixation are to be performed for any subject when CR is suspected or maintained; for light chain MM subjects, serum FLC will also be performed on Day 1 of every cycle, at end of treatment and at follow-up until PD.									
Disease Evaluations (Other)												

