Abbreviations: Anti-HBc=antibodies to hepatitis B core antigen; Anti-HBs=antibodies to hepatitis B surface antigen; C=Cycle; COPD=chronic obstructive pulmonary disease; CR=complete response; CT=computed tomography; d/D=day(s); Dara-SC=daratumumab and recombinant human hyaluronidase for subcutaneous injection; Dara-IV=daratumumab for intravenous formulation; ECOG=Eastern Cooperative Oncology Group; EOT=End of Treatment; FISH=fluorescence in situ hybridization; FLC=free light chain; FUP=Follow-up Phase; HBV=hepatitis B virus; ICF=informed consent form; IV=intravenous; Qlg=quantitative immunoglobulin; MM=multiple myeloma; modified-CTSQ=modified Cancer Therapy Satisfaction Questionnaire; MR=minimal response; MRI=magnetic resonance imaging; PBMC=peripheral blood mononuclear cells; PCR=polymerase chain reaction; PD=progressive disease; PET=positron emission tomography; PR=partial response; rHuPH20=recombinant human hyaluronidase; sCR=stringent CR; SPEP=Serum M-protein quantitation by electrophoresis; UPEP=urine M-protein quantitation by electrophoresis; VGPR=very good partial response; w=weeks.											

- a. For subjects who discontinue study treatment before PD, disease evaluations should continue to be performed at the frequency specified below until confirmed PD, death, start of a new treatment for multiple myeloma, withdrawal of consent to study participation, or end of the study whichever occurs first. Once PD is confirmed subsequent disease assessment time points are not required.
 - Every 4 weeks: SPEP and 24-hour UPEP assessments, and serum calcium corrected for albumin
 - When CR is suspected or maintained: serum FLC, serum and urine immunofixation
 - As clinically indicated: skeletal survey
 Evidence of clinical relapse will also be documented at the time at which it is first detected.
 After PD is documented, survival status, subsequent anticancer treatment, response to subsequent anticancer treatment, date of progression, and information on all new second primary malignancies will be recorded (interview may be conducted by telephone) for all subjects until the end of the data collection period.
- b. To be performed only for subjects with serologic evidence of resolved HBV infection (ie, positive anti-HBs or positive anti-HBc) at Screening, HBV DNA testing by PCR must be performed locally. Performed locally every 4 weeks during treatment, end of treatment visit, and every 4 weeks for up to 6 months after the last dose of study treatment.

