3. STUDY DESIGN AND RATIONALE

3.1. Overview of Study Design

This is a Phase 3, randomized, open-label, active-controlled, multicenter study to demonstrate that the efficacy and pharmacokinetics of Dara-SC are not inferior to those for Dara-IV. The study population will consist of adults diagnosed with multiple myeloma who have received at least 3 prior lines of therapy including a PI and an IMiD, or whose disease is refractory to both a PI and an IMiD. Approximately 480 subjects will be assigned randomly to the Dara-SC group or the Dara-IV group in a 1:1 ratio. The randomization will be stratified by body weight at baseline (≤ 65 kg, 66 kg to 85 kg, >85 kg), number of prior lines of therapy (≤ 4 prior lines versus >4 prior lines), and type of myeloma (IgG versus non-IgG).

[figure not shown]
The study consists of 3 phases: a Screening Phase, a Treatment Phase, and a Follow-up Phase. A diagram of the study design is provided in Figure 1. The Screening Phase will be up to 28 days before randomization. The Treatment Phase will extend from randomization until discontinuation of study treatment. Each subject will be treated until the sponsor confirms that disease progression has occurred for that subject, the subject has unacceptable toxicity, or other reasons (refer to Section 10.1, Discontinuation of Study Treatment). The Follow-up Phase begins immediately following the End-of-Treatment Visit, and will continue until death, loss to follow up, withdrawal of consent for study participation, or end of the data collection period, whichever occurs first.

Treatment cycles are 28 days in length. The dosing schedule for both groups will be weekly for Cycles 1 and 2, every 2 weeks for Cycles 3 to 6, and every 4 weeks thereafter. Subjects who are assigned to the Dara-SC group will receive a fixed dose of Dara-SC 1800 mg (daratumumab 1800 mg co-formulated with rHuPH20 2000 U/mL). Dara-SC will be delivered by SC injection in the abdominal SC tissue in left/right locations, alternating between individual doses. All subjects in the Dara-SC group will be observed for at least 6 hours after the end of the SC injection during Cycle 1 Day 1 and, if deemed necessary by the investigator, after consecutive

injections. Subjects who are assigned to the Dara-IV group will receive Dara-IV 16 mg/kg by IV infusion pump.

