8.1.6. Management of Hepatitis B Virus Reactivation

Primary antiviral prophylaxis is permitted as per local standard of care. Per protocol, HBV DNA testing by PCR is mandatory for subjects at risk for HBV reactivation, see Section 9.7.

For subjects with evidence of positive HBV serology, monitor for clinical and laboratory signs of HBV reactivation during, and for at least 6 months following the end of study treatment. Manage subjects according to current clinical guidelines. Consider consulting a hepatitis disease expert as clinically indicated.

For subjects who develop reactivation of HBV while on study treatment, suspend study treatment and institute appropriate treatment for HBV or follow country-specific clinical guidelines. Resumption of study treatment in subjects whose HBV reactivation is adequately controlled should be discussed with physicians with expertise in managing HBV.

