- a. Providing ABO/RhD compatible, phenotypically (standard or extended phenotyping) or genotypically matched units
- b. Providing ABO/RhD compatible, K-negative units after ruling out or identifying alloantibodies using DTT-treated reagent RBCs

Uncrossmatched, ABO/RhD compatible RBC units should be administered if transfusion is needed emergently as per local blood bank practice.

Despite daratumumab binding to CD38 on erythrocytes, no indication of clinically significant hemolysis has been observed in daratumumab studies. For additional details, refer to the daratumumab Investigator's Brochure (IB daratumumab¹⁰).

HBV DNA Tests

Subjects who are positive for anti-HBc or anti-HBs will undergo testing for hepatitis B DNA by PCR every 4 weeks (each cycle). Subjects who are positive for anti-HBs antibodies due to prior immunization are not required to be monitored by HBV DNA by PCR. During and following study treatment, subjects who have history of HBV infection will be closely monitored for clinical and laboratory signs of reactivation of HBV as specified in the Time and Events Schedule. Subjects with serologic findings suggestive of prior HBV vaccination (anti-HBs positivity as the only serologic marker) AND a known history of prior HBV vaccination do not need to be tested for HBV by PCR and do not need to be followed by repeat HBV PCR. Where required by local law, the result of HBV testing may be reported to the local health authorities.

Subjects benefiting from daratumumab after the data collection period has ended may continue receiving study drug, and HBV DNA testing will be performed as detailed in [Attachment 13](#).

Pulmonary Function Test

Subjects with known or suspected COPD must have a FEV1 test during screening.

Electrocardiogram (ECG)

A 12-lead ECG will be performed as described in the Time and Events Schedule. During the collection of ECGs, subjects should be in a quiet setting without distractions (eg, television, cell phones). Subjects should rest in a supine position for at least 5 minutes before ECG collection and should refrain from talking or moving arms or legs. If blood sampling or blood pressure measurement is scheduled for the same time point as ECG recording, then the procedures should be performed in the following order: ECG(s), blood pressure, blood draw.

Vital Signs

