Attachment 13: Continuation of Treatment After Clinical Cutoff for the Final Analysis (End of the Data Collection Period)

Protocol Amendment 3 will allow those subjects who are benefitting from daratumumab treatment after the clinical cutoff date for the final analysis (end of the data collection period) to continue receiving study drug. The sponsor will ensure that subjects will be able to continue receiving the appropriate formulation of IV or SC daratumumab after the data collection period has ended until the applicable formulation is commercially available or available from another source, or until the study is complete (see Section 17.9.1). The following limited schedule is applicable.

Documentation of assessments performed is required only in the subject file/source notes.

Dosage and Administration

Daratumumab will be administered according to the regimen established prior to Amendment 3 (see Section 6).

Treatment Period

Once the sponsor has notified investigators that the clinical cutoff for the final analysis has been achieved (end of the data collection period), subjects may continue treatment with daratumumab until PD per investigator evaluation, unacceptable toxicity, withdrawal of consent, the investigator decides to stop treatment, or the start of subsequent anticancer therapy. Post-treatment follow-up is not applicable for subjects who discontinue study treatment in this period, except for HBV DNA testing as described below.

Efficacy Evaluations

Investigators should monitor and assess subjects for response to treatment or disease progression according to local institutional practice. The assessments and outcome should be entered in the subject file/source notes.

Safety Laboratory Assessments

Once the data collection period has ended, local hematology labs, chemistry labs, and assessment of vital signs should still be performed on Day 1 of each dosing cycle for consistency with previous cycles and in accordance with good clinical practice. These local laboratory results do not need to be reported to the sponsor.

Safety Reporting

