Once the data collection period has ended, serious adverse events that occur while the subject is receiving study drug and within 30 days after the last dose of study drug will be collected and reported to the sponsor's global medical safety database only via the same serious adverse event reporting process used over the course of the study (see Section 12.3.2). Serious adverse events that occur between the end of the 30-day post-dose period and completion of the study should be reported using the same process if considered by the investigator to be related to study drug. Serious adverse events should also be documented in the subject file/source notes.

Pregnancy reporting should continue as described in Section 12.3.4. The pregnancy should be documented in the subject file/source notes.

HBV DNA Tests

Subjects who are positive for anti-HBc or anti-HBs will undergo testing for HBV DNA by PCR every 4 weeks (± 1 month) after entering this treatment period. Testing will continue for 6 months after the last dose of study treatment. Subjects with serologic findings suggestive of HBV vaccination (anti-HBs positivity as the only serologic marker) and a known history of prior HBV vaccination do not need to be tested for HBV by PCR.

Sample Collection and Handling

There are no PK, immunogenicity, or biomarker assessments during this treatment period, and any sample collection or test for safety or disease evaluation should comply with standard local institution practice. Please note that local bone marrow analysis is required for the assessment of CR.

Case Report Form Completion

No data will be collected in the eCRF during this treatment period.

Source Documentation

At a minimum, the type and level of detail of source data collected should be consistent with that commonly recorded at the site as a basis for standard medical care. This should include: subject identification and study identification, study discussion, documentation of the informed consent process including the date, dates of visits, drug dispensing/return records, and study drug administration information.

INVESTIGATOR AGREEMENT

I have read this protocol and agree that it contains all necessary details for carrying out this study. I will conduct the study as outlined herein and will complete the study within the time designated.

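### Protocol 9.1.4 waives Follow-up Phase procedures at the end of data collection with no HBV exception, so the rest of the 6-month HBV DNA testing is in doubt for at-risk subjects already off treatment

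*Protocol*

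**What the plan says.** - **Section 8.1.6** makes HBV DNA testing by PCR mandatory for subjects at risk of reactivation and refers to Section 9.7. It also asks for monitoring of those with positive HBV serology "during, and for at least 6 months following the end of study treatment". It mentions no data-collection limit.
- **Section 9.7 (HBV DNA Tests)** says that, during and after treatment, subjects with a history of HBV infection are "closely monitored for clinical and laboratory signs of reactivation of HBV as specified in the Time and Events Schedule".
- **Table 1, HBV DNA test row** ("Only for subjects who are positive for anti-HBc or anti-HBs") has an entry after the End-of-Treatment visit, in a Follow-up Phase column. Footnote b sets its frequency: "every 4 weeks for up to 6 months after the last dose of study treatment".
- **Section 3.1** ends the Follow-up Phase at the first of death, loss to follow-up, "withdrawal of consent for study participation, or end of the data collection period, whichever occurs first".
- **Section 9.1.4** adds: "Continuation of Follow-up Phase study procedures is not required once the end of the data collection period is reached". The End of Trial eCRF page is completed at that point for subjects still in follow-up.
- **Attachment 13**, for subjects who stay on study drug after the cutoff, says: "Post-treatment follow-up is not applicable for subjects who discontinue study treatment in this period, except for HBV DNA testing as described below". On the tests themselves it says: "Testing will continue for 6 months after the last dose of study treatment".

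**The concern.** The requirement in 8.1.6 leads to 9.7, 9.7 leads to Table 1, and Table 1 puts the post-treatment tests in a phase that 3.1 closes and 9.1.4 waives. A site applying 9.1.4 literally could close a subject out and stop PCR testing inside the 6-month window.

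The protection then depends on which side of an administrative date the last dose falls. A subject who stops drug shortly after the cutoff has an explicit instruction to test for 6 months. A subject who stopped a month or more before it has a waiver.

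Scheduled PCR is there to detect reactivation. As Table 1 reads in the extracted text, chemistry ends at the End-of-Treatment visit, so no other scheduled laboratory test would pick up reactivation after that. Continued follow-up of related or unresolved serious adverse events deals with events already recognised.

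**Working it through.** **Who is covered after the cutoff**

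| Subject at the end of data collection | Text that applies | HBV DNA testing to 6 months? |
|---|---|---|
| Still on study drug, stops later | Attachment 13 | Yes, explicit |
| In Follow-up Phase, last dose 4 to under 24 weeks earlier | 8.1.6 and Table 1 footnote b; 3.1 and 9.1.4 | In conflict |
| In Follow-up Phase, last dose 24 weeks or more earlier | 8.1.6 | No 4-weekly test left |

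Sections 9.1.5 and 9.7 refer to Attachment 13 only for subjects who continue drug, so they do not bring in the middle row.

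**Tests at stake per subject**

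- Six months is 365.25 / 2 / 7 = 26.1 weeks.
- Four-weekly tests after the last dose fall at weeks 4 (End-of-Treatment visit), 8, 12, 16, 20 and 24.
- The Follow-up Phase starts after the End-of-Treatment visit (Section 3.1), normally 4 weeks after the last dose (Section 9.1.3).

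| Weeks from last dose to cutoff | 4 | 8 | 12 | 16 | 20 | 24 |
|---|---|---|---|---|---|---|
| Scheduled tests still to come | 5 | 4 | 3 | 2 | 1 | 0 |

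If last doses are spread evenly over weeks 4 to 24, each 4-week band has equal weight and the mean is (5 + 4 + 3 + 2 + 1) / 5 = 3 tests.

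**How many subjects**

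The documents give no figure, so this is an illustration under assumptions: 480 subjects enrolled evenly over 12 months, exponential time on treatment with median 4 to 10 months, and 5% to 20% with resolved-HBV serology. From the protocol: cutoff *C* = 24 months after the last randomization, or earlier if median OS is reached in both arms.

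With λ = ln 2 / median, and 4 and 24 weeks equal to 0.92 and 5.52 months:

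N = 480 × [(e^(−λC) − e^(−λ(C+12))) / (12λ)] × (e^(5.52λ) − e^(0.92λ))

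For median 10 months and *C* = 24, λ = 0.0693. The bracket is (0.1895 − 0.0825) / (12 × 0.0693) = 0.1286, and the last factor is 1.466 − 1.066 = 0.400. N = 480 × 0.1286 × 0.400 = 24.7.

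| Scenario | Subjects in the window, median 4 / 6 / 8 / 10 months | At risk (5% of lowest to 20% of highest) |
|---|---|---|
| 24-month cutoff | 4.5 / 12.7 / 19.8 / 24.7 | 0.2 to 4.9 |
| Same, deaths removed, survival after last dose median 5 months | 2.8 / 8.0 / 12.6 / 15.8 | 0.1 to 3.2 |
| Same, deaths removed, median 9 months | 3.5 / 9.8 / 15.3 / 19.2 | 0.2 to 3.8 |
| Cutoff at 20.1 months | 8.9 / 19.9 / 27.7 / 32.4 | 0.4 to 6.5 |
| Cutoff at 20.1 months, deaths removed (5 to 9 months) | 5.5 (lowest) to 25.2 (highest) | 0.3 to 5.0 |

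The 5-to-9-month survival range is taken from Protocol 1.1, and 20.1 months is the median OS in MMY2002 (Protocol 1.2.1.1). Changing enrolment to 9 or 20 months at the 24-month cutoff, without removing deaths, gives 5.4 to 27.1 or 3.0 to 19.7 subjects.

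**The case against.** The strongest reply is that the texts can be read together. According to the amendment log, Amendment 3 introduced the data-collection cutoff and, in the same amendment, Section 8.1.6 and footnote b. It attached the cutoff by name to many items, including disease evaluations, the satisfaction questionnaire, concomitant medication and adverse events, but not to 8.1.6 or footnote b. A specific safety instruction with its own end point would normally prevail over a general waiver, and 9.1.4 never mentions HBV. On that reading the duty to test survives and only a cross-reference is missing.

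That reading is available, and part of it stands: 9.1.4 does not forbid testing and 8.1.6 still applies. It is not the only reading. The schedule that 8.1.6 relies on, through 9.7, lies in the waived phase, and 9.1.4 also closes these subjects out with the End of Trial page. Attachment 13, from the same amendment, shows that the sponsor thought HBV testing needed an explicit exception when post-treatment follow-up was dropped. The matching words are absent from 9.1.4, and no reason is given for treating the two groups differently.

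Three further points are fair:

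- The sentence in 8.1.6 making PCR mandatory and the one setting 6 months are separate. The 4-weekly PCR over 6 months comes from footnote b through 9.7.
- The survival range describes heavily pretreated or refractory patients in general, not patients stopping daratumumab, and reaching a Kaplan-Meier median does not require every subject to have been followed that long. The counts are orders of magnitude only.
- HBV DNA-positive subjects were excluded at screening, which lowers the risk but does not remove the reason for monitoring.

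**Conclusion.** The concern holds, at minor severity. For at-risk subjects in the Follow-up Phase at the cutoff with a last dose 4 to 24 weeks earlier, the protocol is in conflict on whether the remaining HBV DNA tests are required. It does not clearly remove them.

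The reading of the text rests on the documents alone. The number affected rests on assumed enrolment, time on treatment, serology prevalence and survival after the last dose. It is small, possibly zero: about 0 to 5 at-risk subjects at the 24-month cutoff, and up to 6 or 7 under the least favourable scenario shown. Each would have 1 to 5 tests in doubt. No endpoint, estimand, sample size or error rate is touched; the matter is one of subject safety. An early End-of-Treatment visit, held before subsequent therapy, could open the window before week 4.

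**What to change.** Add one exception to the 9.1.4 sentence, along these lines: *except that, for at-risk subjects in the Follow-up Phase when data collection ends, HBV DNA testing continues every 4 weeks until 6 months after the last dose, recorded in source notes only.*

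As an optional consistency edit, change footnote b of Table 1 from up to 6 months to a full 6 months, in line with 8.1.6 and Attachment 13.

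The cost is at most 5 local PCR tests per affected subject, all already in the schedule. At 5 at-risk subjects and a mean of 3 tests this is 15 tests in total; at 6.5 subjects it is about 20. No eCRF data and no change to any analysis are needed.
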